7.1.3. ADVERSE EVENTS

Solicited Adverse Events:

Daily recording of solicited adverse events: for diary cards indicating the presence or absence of solicited adverse events, for studies using paper diaries which have questions in the CRF indicating the presence or absence of solicited events the following rules are applicable:

- Denominators for the summary of administration site (or systemic) solicited adverse events will be calculated using the number of participants who respond "Yes" or "No" to the question concerning the occurrence of administration site (or systemic) adverse events.
- When a specific solicited adverse event is marked as having not occurred following a specific vaccination (i.e., SDTM FA.FAOCCUR=N for the specified post-vaccination period for the adverse event in question), all daily measurements will be imputed as Grade 0.
- When a specific solicited adverse event is marked as having occurred following a specific vaccination (i.e., SDTM FA.FAOCCUR=Y for the specified post-vaccination period for the adverse event in question), any missing daily recordings will be given imputed values to allow them to contribute to the 'Any' rows but not to specific grade rows of the solicited adverse event summary tables.
- When the occurrence of a specific solicited adverse event is not present (i.e. SDTM FA.FAOCCUR is neither Y nor N for the specified post-vaccination period for the symptom in question) but the group of solicited adverse events (administration site or systemic) is marked as having occurred (i.e. SDTM FA.FAOCCUR=Y), all missing daily recordings will be given imputed values to allow them to contribute to the 'Any' rows but not to specific grade rows of the solicited adverse event summary tables.

The following table shows how participants contribute to each category for a specific solicited adverse event over the Day X to Day Y post-vaccination period:

Document:	\dccar2dnetvnasc01p-lan1.quintiles.net\cp_ops\PROJECTS\Glaxo SmithKline\GSK205480_HAB61752\SAP		
Author:	PPD	Version Number:	1.0

Template No: CS_TP_BS016 – Revision 7
Effective Date: 01Nov2021

Reference: CS_WI_BS005

Solicited adverse event category	Participants included in the calculation of the numerator
Any	All participants with at least one occurrence of the adverse event at grade 1, grade 2, or grade 3 between Day X and Day Y or with the adverse event marked as present and at least one missing daily recording between Day X and Day Y

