Grade 1	All participants with at least one occurrence of the adverse event at grade 1, between Day X and Day Y
Grade 2	All participants with at least one occurrence of the adverse event at grade 2 between Day X and Day Y
Grade 3	All participants with at least one occurrence of the adverse event at grade 3 between Day X and Day Y

Unsolicited adverse events

Unsolicited adverse event summaries are including serious adverse events unless specified otherwise. Missing severity, relationship with study vaccine, and outcome of unsolicited adverse events will not be replaced and will appear as 'UNKNOWN' in all statistical listings.

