7.2.6. COUNTING RULES FOR OCCURRENCES OF SOLICITED ADVERSE EVENTS

When the occurrences of solicited adverse events are summarized, each event recorded as having occurred during a specific period will be counted as only one occurrence regardless of the number of days on which it occurs.

For a given participant and the analysis of solicited symptoms within 7 days post-vaccination, missing or non-evaluable measurements will not be replaced. Therefore, the analysis of the solicited adverse events will include only vaccinated participants for doses with documented safety data (i.e., diary card completed). A diary card is considered complete when it has data recorded for all 7 days post vaccination. More specifically the following rules will be used:

- Participants who documented the absence of a solicited symptom after one dose will be considered not having that symptom after that dose.
- Participants who documented the presence of a solicited symptom and fully or partially recorded daily measurement over the solicited period will be included in the summaries at that dose and classified according to their maximum observed daily recording over the solicited period.
- Participants who documented the presence of a solicited symptom after one dose without having recorded any daily measurement will be assigned the value 'UNKNOWN'.
- Doses without diary cards documented will be excluded.

Document: \\dccar2dnetvnasc01p-lan1.quintiles.net\cp_ops\PROJECTS\Glaxo SmithKline\GSK205480_HAB61752\SAP
Author: PPD Version Number: 1.0
Version Date: 25OCT2022

Template No: CS_TP_BS016 – Revision 7
Effective Date: 01Nov2021

Reference: CS_WI_BS005

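### SAP 7.1.3 and 7.2.6 give incompatible counting rules for solicited events: unanswered symptoms can enter symptom-level 'Any' rows, and Grade 1 and 2 rows can overlap higher grades

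*SAP*

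**What the plan says.** SAP 7.1.3 uses two levels of occurrence flag: one for each symptom and one for its group (administration site or systemic). The denominator is set at group level, as the participants who answer Yes or No "to the question concerning the occurrence of administration site (or systemic) adverse events". The fourth rule covers a symptom whose flag "is neither Y nor N for the specified post-vaccination period for the symptom in question) but the group of solicited adverse events" is marked as having occurred. In that case "all missing daily recordings will be given imputed values to allow them to contribute to the 'Any' rows but not to specific grade rows".

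A numerator table follows, introduced by "The following table shows how participants contribute to each category for a specific solicited adverse event". Its 'Any' row takes participants with an occurrence at grade 1, 2 or 3, or "with the adverse event marked as present and at least one missing daily recording between Day X and Day Y". Its Grade 1 row takes "All participants with at least one occurrence of the adverse event at grade 1, between Day X and Day Y", its Grade 2 row takes "All participants with at least one occurrence of the adverse event at grade 2 between Day X and Day Y", and Grade 3 follows the same pattern.

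SAP 7.2.6 covers the same seven-day data. It leaves missing or non-evaluable values unreplaced. Participants with a documented symptom and at least some daily values are "classified according to their maximum observed daily recording over the solicited period". It has rules for documented absence, documented presence and undocumented diary cards, but none for a symptom marked neither way. Protocol 10.3.9.1 scores redness, swelling and fever by maximum intensity.

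**The concern.** Two programmers could follow the SAP faithfully and print different tables.

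On the first matter, a participant who reports a headache has the systemic group at Y. If the arthralgia line has no Y/N answer and no daily values, the fourth rule puts that participant in the arthralgia 'Any' row, although nothing was reported about arthralgia and the headache already explains the group answer. The numerator table and 7.2.6 would both leave the participant out.

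On the second, a reaction that peaks at Grade 3 and resolves through Grades 2 and 1 can enter three rows under 7.1.3 but only one under 7.2.6.

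Solicited events are the first two primary safety endpoints. SAP 16.1 tabulates each individual symptom with an exact 95% CI, and protocol 9.1 says the results will inform the choice of formulation. The groups are small, so one participant moves a percentage visibly.

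**Working it through.** The plan states no figure on this point, so the check sets the rules side by side and then applies them to counts.

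**Inputs.** Group sizes from protocol Table 4: 24 in each full-dose group; 12 in each low-dose group and in the Step 2 control; 6 in each Step 1 control. Intervals are Clopper-Pearson (SAP 6.1). The same interval code reproduces protocol Table 15, for example 10/21 = 47.6% (25.7 to 70.2). The number of blanks is an assumption.

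**1. A symptom with no Y/N answer and no daily values, group flag Y, another symptom reported**

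| Rule | Result for the blank symptom |
|---|---|
| 7.1.3, fourth rule | In the 'Any' row, in no grade row |
| 7.1.3, numerator table | Out: neither graded nor marked present |
| 7.2.6 | Not replaced, so not counted |

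The denominator is group-level, so the participant stays in it. Counting the blank adds 1/n: 1/24 = 4.2 points, 1/12 = 8.3, 1/6 = 16.7.

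With x true reports and one blank, 7.1.3 prints (x+1)/n. Removing the blank from numerator and denominator gives x/(n−1).

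| n | x | 7.1.3, blank counted | Blank removed |
|---|---|---|---|
| 24 | 0 | 1/24 = 4.2% (0.1 to 21.1) | 0/23 = 0% (0 to 14.8) |
| 12 | 0 | 1/12 = 8.3% (0.2 to 38.5) | 0/11 = 0% (0 to 28.5) |
| 6 | 0 | 1/6 = 16.7% (0.4 to 64.1) | 0/5 = 0% (0 to 52.2) |
| 24 | 2 | 3/24 = 12.5% (2.7 to 32.4) | 2/23 = 8.7% (1.1 to 28.0) |
| 12 | 2 | 3/12 = 25.0% (5.5 to 57.2) | 2/11 = 18.2% (2.3 to 51.8) |

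The rule acts only where the group flag is Y, so its expected effect grows with reactogenicity. If a proportion g of the arm has group Y and a proportion b of symptom lines is blank, independently, about g × b is added per symptom. For an assumed b of 1% to 5%, g = 60% gives 0.6 to 3.0 points and g = 30% gives 0.3 to 1.5. At n=24 and g = 60% that is 0.14 to 0.72 participants per symptom.

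For fever there is a further mismatch. SAP 16.1.3 defines fever as 38.0°C or above, and SAP 16.1 tabulates it in 0.5°C bands. A fever counted from a blank has no temperature to place in any band.

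**2. Grade rows**

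Assume 24 participants, of whom 9, 6 and 3 have maximum grade 1, 2 and 3. 'Any' is 18/24 = 75%.

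| Row | Maximum grade (7.2.6) | 7.1.3, if all pass through lower grades |
|---|---|---|
| Grade 1 | 9/24 = 37.5% | (9+6+3)/24 = 75% |
| Grade 2 | 6/24 = 25% | (6+3)/24 = 37.5% |
| Grade 3 | 3/24 = 12.5% | 3/24 = 12.5% |
| Sum | 75% | 125% |

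This is the upper end. If nobody passes through a lower grade, the columns agree. So the Grade 1 row lies between 9 and 18, the Grade 2 row between 6 and 9, and Grade 3 is fixed.

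**3. What cannot move.** The group-level rate of at least one event is unchanged, because the group flag is already Y. Grade 3 is the top grade, so any occurrence at Grade 3 is the maximum, and imputed values enter no grade row. Holding rules 2a and 2b (protocol Table 11) count Grade 3 events only.

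**The case against.** - **The trigger is narrower than it looks.** A reader might infer that every unanswered symptom becomes an event once another symptom is reported. The text does not say that. The trigger is the group flag, and only missing daily recordings are imputed. A blank flag with temperatures below 38.0°C on file leaves nothing to impute. If every other symptom is N, the blank is the only listed symptom that can explain the group Y, and counting it is reasonable. This stands and shapes the fix.
- **Blanks should be rare.** There are diary reminder calls, transcription at Visits 2 and 5 and source data verification, and 7.2.6 calls a diary complete only with data for all seven days. This limits the likely size. It does not settle which rule applies, and 7.2.6 itself admits partly recorded symptoms.
- **Counting blanks is conservative in a first-in-human study.** That is a fair aim, but a labelled sensitivity row serves it without mixing blanks into the main symptom rates, where they weigh more in the arm with more group-level reporting.
- **The grade rows may mean one occurrence per event.** SAP 7.2.6 counts an event once regardless of its number of days, so the table could be read as one event at its maximum grade. That reading is possible, and the SAP's output templates, which are not in the public documents, may adopt it. But the 7.1.3 table does not mention a maximum, and its 'Any' row refers to daily recordings.
- **The severity profile is not lost.** A reader might infer that the grade rows become unreadable. Grade 3 is exact, and in the worked example the maximum grades follow by subtraction (18−9, 9−3, 3). In general, though, the printed rows would not show how many participants passed through each lower grade.

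**Conclusion.** The inconsistency is real and should be resolved before the tables are programmed. It is confined to symptom-level 'Any' rows and Grade 1 and 2 rows. A reader might infer that the headline primary safety rates, the Grade 3 rates or the dose-escalation safeguards are inflated; on the SAP text they are not.

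Each qualifying blank (no Y/N answer, missing daily values, group Y) adds 4.2, 8.3 or 16.7 points at n = 24, 12 or 6. The total cannot be stated, because the documents give no blank rate; the 1% to 5% range above is only an illustration. The grade overlap depends on how many reactions pass through lower grades, which is also not given. The contradictions between the rules depend on neither assumption.

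**What to change.** In SAP 7.1.3:

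1. Restrict the fourth rule to the case where no other symptom in the group is recorded as present, so that the blank is what can explain the group Y. Say what happens if several symptoms are blank and none is present. Add the same exception to the numerator table and cross-refer to it from the no-replacement sentence in 7.2.6.
2. Otherwise, treat a symptom with neither a Y/N answer nor daily values as not reported: out of that symptom's numerator and denominator, with the number shown. Where daily values exist, classify from them.
3. Give the count with all blanks as events in a labelled sensitivity row.
4. Define the Grade 1, 2 and 3 rows by each participant's maximum grade, as in 7.2.6.

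The cost is SAP wording and programming, with no change to data collection. The downside is that symptom denominators may differ slightly from the group denominator, which a footnote can explain. SAP version 1.0 rests on the protocol of 23 August 2022 and two amendments have followed, so a SAP revision is a natural place for the change.

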7.2. DATA DERIVATION

7.2.1. BODY MASS INDEX

BMI (kg/m²) = weight (kg)/height (m²)

7.2.2. AGE AT VACCINATION IN YEARS

When age at vaccination is to be displayed in years, it will be calculated as the number of complete calendar years between the 15MMYY and the date of vaccination, divided by 365.25. Date of birth is collected only by means of month and year of birth in the database, therefore, by rules defined in Section 7.1.1, 15th day of month is substituted for the day. For example:

DOB = 15SEP1983, Date of vaccination = 14SEP2018 -> Age = 34.998 years

DOB = 15SEP1983, Date of vaccination = 15SEP2018 -> Age = 35.001 years

7.2.3. ONSET DAY

The onset day for an event (e.g., AE, medication, vaccination) is the number of days between the last study vaccination and the start date of the event. This is 1 for an event occurring on the same day as a vaccination (and reported as starting after vaccination).

Document: \\dccar2dnetvnasc01p-lan1.quintiles.net\cp_ops\PROJECTS\Glaxo SmithKline\GSK205480_HAB61752\SAP
 Author: PPD Version Number: 1.0
 Version Date: 25OCT2022

Template No: CS_TP_BS016 – Revision 7
 Effective Date: 01Nov2021

Reference: CS_WI_BS005

7.2.4. DURATION OF EVENTS

The duration of an event with a start and end date will be the number of days between the start and end dates plus one day, i.e., an event that starts on 03MAR2018 and ends on 12MAR2018 has a duration of 10 days.

The duration of solicited events will be calculated as the difference between the dates when the first and last symptom reported at grade 1 or higher were observed plus one day (also including days after Day 7 if event is still ongoing).

7.2.5. COUNTING RULES FOR COMBINING SOLICITED AND UNSOLICITED ADVERSE EVENTS

For output combining solicited and unsolicited adverse events, all serious adverse events will be considered systemic events since the administration site flag is not included in the expedited adverse event CRF pages.

Multiple events with the same preferred term which start on the same day are counted as only one occurrence.

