1a	Death or any life-threatening SAE regardless of causality	≥1	≥1	≥1
1b	Any non-life-threatening SAE that cannot be reasonably attributed to a cause other than vaccination as per Investigator or Sponsor assessment	≥1	≥1	≥1
1c	Any withdrawal from the study (by Investigator or participant request) following a Grade 3 AE	≥1	≥1	≥1
1d	Any solicited administration-site event or solicited systemic event leading to hospitalisation, OR Necrosis at the injection site, Each with an event onset within the 7-day post-vaccination period	≥1	≥1	≥1
2a	Any Grade 3 solicited administration-site events (lasting 48h or more as Grade 3), with an event onset within each 7-day post-vaccination period	≥3	≥3	≥6
2b	Any Grade 3 solicited systemic events (lasting 48h or more as Grade 3), with an event onset within each 7-day post-vaccination period	≥2	≥2	≥3
2c	Any Grade 3 unsolicited AE, which can be reasonably attributed to the vaccination as per Investigator or Sponsor assessment, with an event onset within each 7-day post-vaccination period OR Any Grade 3 or above abnormality* in pre-specified haematological or biochemical laboratory parameters collected at 7 days post-vaccination period	≥1**	≥1**	≥2

AE=adverse event, SAE=serious adverse event

*Refer to Section 10.9 for the grading scales to the pre-specified laboratory parameters

**The Investigator should inform IQVIA CRA and Medical Monitor immediately if an event occurs and should follow instruction as applicable to holding rules 1a-1d.

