10.3.2. Definition of an SAE**An SAE is any untoward medical occurrence that:**

- a. Results in death.

- b. Is life threatening

Note: The term 'life-threatening' in the definition of 'serious' refers to an event in which the participant was at risk of death at the time of the event. It does not refer to an event, which hypothetically might have caused death, had it been more severe.

- c. Requires hospitalisation or prolongation of existing hospitalisation

Note: In general, hospitalisation signifies that the participant has been admitted at the hospital or emergency ward for observation and/or treatment that would not have been appropriate in the physician's office or in an out-patient setting. Complications that occur during hospitalisation are also considered AEs. The event will also be considered serious if a complication prolongs hospitalisation or fulfils any other serious criteria. When in doubt as to whether 'hospitalisation' occurred or was necessary, the AE should be considered serious.

- d. Results in disability/incapacity

Note: The term disability means a substantial disruption of a person's ability to conduct normal life functions. This definition is not intended to include experiences of relatively minor medical significance such as uncomplicated headache, nausea, vomiting, diarrhoea, influenza like illness, and accidental trauma (e.g., sprained ankle) which may interfere or prevent everyday life functions but do not constitute a substantial disruption.

e. Is a congenital anomaly/birth defect in the offspring of a study participant
f. Abnormal pregnancy outcomes (e.g., spontaneous abortion, foetal death, stillbirth, congenital anomalies, ectopic pregnancy)
g. Other situations Medical or scientific judgement must be exercised in deciding whether reporting is appropriate in other situations. Important medical events that may not be immediately life threatening or result in death or hospitalisation but may jeopardise the participant or require medical or surgical intervention to prevent one of the other outcomes listed in the above definition should be considered serious. Examples of such events are invasive or malignant cancers; intensive treatment in an emergency room or at home for allergic bronchospasm; blood dyscrasias; and convulsions that do not result in hospitalisation.

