16.1. ADVERSE EVENTS

The analysis of solicited adverse event will be performed in the Solicited Safety Set. The percentage of participants with at least 1 administration site AE (solicited and unsolicited), with at least 1 systemic AE (solicited and unsolicited) and with any AE during the 7-day or the 28-day follow-up period, for each step, will be tabulated with exact 95% CI after each vaccination and overall. The same calculations will be performed for symptoms rated as grade 3 (severe). This combined analysis of solicited and unsolicited AEs will be performed on the Exposed Set as requested for public disclosure. Solicited events and unsolicited AEs will be coded by MedDRA.

The percentage of doses followed by at least 1 administration site AE and by at least 1 systemic AE will be tabulated, overall vaccination course, with exact 95% CI. The same computations will be done for Grade 3 AEs, any AEs considered related to vaccination, any Grade 3 AEs considered related to vaccination and any AEs resulting in a medically attended visit.

The percentage of participants/doses reporting each individual solicited administration site and systemic AE during the 7-day follow-up period will be tabulated with exact 95% CI as follows:

- Over the 2 doses, the percentage of participants with the symptom and its exact 95% CI.
- Over the 2 doses, the percentage of doses with the symptom and its exact 95% CI.
- At each study dose (visit), the percentage of participants with the symptom and its exact 95% CI.

Percentage of participants with at least one fever event will be reported per grade (as per protocol scale) and per 0.5°C cumulative increments as from $\geq 38^{\circ}\text{C}$ to $\geq 40^{\circ}\text{C}$

Solicited events ongoing after the observation period reported by maximum intensity will be left out of summary tables and only reported in solicited AE listings. Any solicited event with onset day greater than solicited period (i.e., 7 days) will be reported as unsolicited AE and will be included in unsolicited summary tables and listings.

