The analysis of unsolicited adverse event will be performed in the Unsolicited Safety Set. The verbatim reports of unsolicited symptoms will be reviewed by a physician and the signs and symptoms will be coded per the Medical Dictionary for Regulatory Activities (MedDRA), Version 25.0. Every verbatim term will be matched with the appropriate preferred term (PT). The percentage of participants with unsolicited AEs within 28 days after any doses with its exact 95% CI will be tabulated by group, step and by MedDRA preferred term. Similar tabulation will be done for Grade 3 unsolicited AEs, for unsolicited AEs that resulted in a medically attended visit, for Grade 3 and causally related unsolicited

Document: \\dccar2dnetvnasc01p-lan1.quintiles.net\cp_ops\PROJECTS\Glaxo SmithKline\GSK205480_HAB61752\SAP
Author: PPD Version Number: 1.0
Version Date: 25OCT2022

Template No: CS_TP_BS016 – Revision 7
Effective Date: 01Nov2021

Reference: CS_WI_BS005

AEs and for unsolicited AEs causally related to vaccination. These tabulations will include System Organ Class (SOC) and SOC/PT analyses.

The number of participants who experienced at least 1 SAE after any dose, from dose 1 until 28 days post second dose (Day 197) and from Day 198 until Day 337 will be reported by treatment.

The following summaries for COVID-19 infections will be presented:

- Number of participants with an AE of suspected, probable or confirmed assessment of COVID-19 infection
- Number of participants who had a COVID-19 diagnosis test performed and the number of participants with positive, negative or indeterminate results
- Incidence of COVID-19 as AEs and SAEs

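### In the combined solicited-plus-unsolicited tables, SAP 7.2.5 counts a serious injection-site event as systemic because a form lacks a site flag

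*SAP*

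**What the plan says.** SAP 7.2.5 sets the rule and limits its scope to outputs that combine solicited and unsolicited AEs. In those outputs, "all serious adverse events will be considered systemic events since the administration site flag is not included in the expedited adverse event CRF pages". The reason given is a limitation of the form. The following sentence treats events that share a preferred term and a start day as one occurrence.

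The output concerned is described in SAP 16.1: "The percentage of participants with at least 1 administration site AE (solicited and unsolicited), with at least 1 systemic AE", and with any AE, over 7 or 28 days, after each vaccination and overall, with a Grade 3 version. It uses the Exposed Set and is tied to public disclosure. The next paragraph of 16.1 adds percentages of doses followed by an administration-site or a systemic AE, including related and medically attended events. That paragraph is not itself labelled as combined output.

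Two protocol sections show that serious local events were contemplated. Holding rule 1d in Table 11 covers "Any solicited administration-site event or solicited systemic event leading to hospitalisation, OR Necrosis at the injection site". Section 10.3.2 makes an event serious if, among other criteria, it "Requires hospitalisation or prolongation of existing hospitalisation".

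**The concern.** The rule assigns a body location according to which form was filled in. For a local event that is serious, the assignment is wrong, and neither SAP 7.2.5 nor SAP 16.1 provides a correction.

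The affected row has no direct substitute. The solicited administration-site events are pain, redness and swelling only (Protocol Table 18), so necrosis as such is not counted there. A solicited symptom that starts after the 7-day period is reported as unsolicited (SAP 16.1). The unsolicited tables are by system organ class and preferred term, with no local/systemic split described. The combined table is thus the only participant-level summary described in the SAP that counts administration-site events including unsolicited ones. At stake is whether the published local row shows zero or one when a single serious local reaction has occurred.

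**Working it through.** No figure in the documents depends on this rule, so there is nothing to reproduce. The check has two parts.

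**1. What the rule does to one serious local event within the 7- or 28-day window**

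| Where the event is recorded | Administration-site row | Systemic row |
|---|---|---|
| Expedited page only; participant has no other event in either row | One too few | One too many |
| Expedited page only; participant has another local event in that row | Correct | One too many, unless the participant has another systemic AE |
| Diary and expedited page | Not determined | Not determined |

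The first two lines follow because the rows count participants with at least one event. The condition is applied row by row: a participant with mild diary-recorded pain stays in the any-grade local row but could still be missing from the Grade 3 local row.

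The third line is open because solicited events come from the diary (Protocol 10.3.8), SAEs also go on the expedited report (Protocol 8.3.3), and the SAP does not say that the diary record is dropped. The one-occurrence rule in SAP 7.2.5 does not say which record survives. The participant could stay in the local row and also enter the systemic row, or could move to the systemic row alone.

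**2. Size of a one-participant change**

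Inputs are the planned group sizes from Protocol Table 4 (investigational groups of 12, 12, 24 and 24; controls of 6, 6 and 12) and the Clopper-Pearson 95% interval from SAP 6.1. The change is 1/n. For a count of zero, the upper limit is 1 − 0.025^(1/n). For a count of one, the lower limit is 1 − 0.975^(1/n) and the upper limit is the 97.5% quantile of a Beta(2, n−1) distribution.

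| n | Local row under the rule | Local row by actual site | Change |
|---|---|---|---|
| 24 | 0/24 = 0.0% (0.0 to 14.2) | 1/24 = 4.2% (0.1 to 21.1) | 4.2 points |
| 12 | 0/12 = 0.0% (0.0 to 26.5) | 1/12 = 8.3% (0.2 to 38.5) | 8.3 points |

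The table assumes that nobody else in the group is in the row. In a Step 1 control group the change would be 1/6 = 16.7 points, but those groups do not bear on the comparison of formulations with and without Alum. If the rule also reaches the dose-level tables, 24 participants with two doses give up to 48 doses, and one event is 1/48 = 2.1 points.

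**3. Whether the missing flag forces the rule**

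It does not. SAP 16.1 has solicited and unsolicited events coded in MedDRA and the unsolicited verbatim reports reviewed by a physician. SAP 7.1.3 includes SAEs in the unsolicited summaries unless otherwise specified. SAP 7.2.5 already uses the preferred term to remove duplicates in this same output.

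**The case against.** The rule is prespecified, its reason is given, and no other section contradicts it. It covers one family of outputs. A serious local event still appears under its own preferred term, in the SAE counts (SAP 16.1) and in the SAE listing (SAP 16.1.2). All of that stands, and it is why the point is minor.

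A reader might infer more, in three ways that the documents do not support:

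- **That serious local reactions drop out of local tolerability reporting or of safety oversight.** The primary endpoint counts solicited administration-site events in the Solicited Safety Set (Protocol 9.4.1), separately from the combined output. Holding rule 1d is monitored continuously by the Investigator (Protocol 8.2.2.3), not from these tables. Necrosis is an SAE only if it meets a criterion in Protocol 10.3.2; non-serious necrosis is outside the SAP rule.
- **That every such event moves both rows.** A diary-recorded local event can keep the participant in the local row, and another systemic AE leaves the systemic row unchanged.
- **That the combined rows are where formulations with and without Alum will be compared.** The SAP ties them to public disclosure and says nothing of that kind.

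It is also fair to say that a preferred term identifies the site only as well as the verbatim report allows. That is a reason to add medical review of unclear terms. It does not justify classing every SAE as systemic.

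**Conclusion.** The concern holds within a narrow scope. In the combined outputs of SAP 7.2.5 and 16.1, a serious administration-site event recorded only on the expedited page is counted in the wrong row, and the handling of an event on both records is undefined.

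One event changes a participant-level administration-site row by at most 4.2 points (n=24) or 8.3 points (n=12). This assumes planned group sizes as denominators, an event inside the follow-up window, and no other event for that participant in the row. The systemic row changes only if the participant has no other systemic AE. The documents give no expected rate of serious local events; they should be rare, and the rule may never operate. The change is worth making because it costs little, but it is low priority.

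**What to change.** Replace the sentence in SAP 7.2.5, for combined outputs only, with a rule of this kind:

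- An SAE is classified as administration-site or systemic according to its MedDRA preferred term, using a prespecified list of administration-, injection- and vaccination-site terms.
- SAEs whose term leaves the site unclear are classified by medical review, blinded to study group and completed before the analysis concerned.
- An event recorded on both the diary and the expedited page is counted once, in the administration-site row if it is local.

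The SAP should also say whether the dose-level tables in 16.1 follow the same rule.

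The term list should be agreed before the first interim analysis, because the sponsor is no longer considered blinded after it (Protocol 6.3.4 and glossary). The cost is a few SAP sentences, a short term list and a brief medical review, with no new data collection. The SAP is based on the protocol of 23 August 2022, and two amendments have followed, so the change could go into any update made for those.
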